6.3 Specimen Collection, Preparation, Handling and Shipping

6.3.1 Specimen collection

Oral Cavity: Specimens will be collected from multiple locations within the mouth, saliva, soft tissue and hard tissue sites. Saliva will be collected from the floor of the mouth with a calibrated pipette. Soft tissue specimens will be collected from the tongue dorsum, hard palate, buccal mucosa, keratinized (attached) gingiva, palatine tonsils and throat using sterile Catch-All™ Sample Collection Swabs. Supragingival plaque and subgingival plaque will be collected from a minimum of four molar teeth using a Gracey curette. See the Manual of Procedures for details of specimen collection.

Skin and Nasal Cavity: Specimens will be collected from the retroauricular crease of both ears and from the antecubital fossa (inner elbow) of both arms, by rubbing with sterile Catch-All™ Sample Collection Swabs. Specimens will be collected from the anterior right and left nares, using a sterile applicator. See the Manual of Procedures for details of specimen collection.

Gastrointestinal tract: Stool from a single bowel movement will be collected by the subject. Subjects will be provided with a materials kit for collecting stool prior to the baseline visit. Subjects will bring collected stool to the baseline visit. Stool will be collected within 24 hours before the baseline visit and kept cool using the provided frozen gel packs and Styrofoam box. See the Manual of Procedures for details of specimen collection.

Vagina: Specimens will be collected from the posterior fornix of the vagina, the midpoint of the vagina, and the vaginal introitus using sterile Catch-All™ Sample Collection Swabs. See the Manual of Procedures for details of specimen collection.

Blood: Whole venous blood specimens will be collected using appropriate aseptic technique. At the baseline sampling visit, 30 mL of blood will be collected in three 10-mL tubes. Two tubes will be used to collect and store whole blood for human DNA isolation and possible later creation of cell lines. These specimens will be sent to Coriell Institute for Medical Research. One tube will be used to collect blood from which serum will be separated and stored at the clinical site. The serum may be used for future research studies related to the human microbiome (such as measurements of immune responses to organisms identified in the microbiome), and, with the subject's permission, for studies not necessarily related to the human microbiome. See the Manual of Procedures for details of specimen collection.

6.3.2 Specimen handling, preparation and nucleic acid extraction

See the Manual of Procedures for protocols for handling the clinical specimens and extracting microbial nucleic acids.

6.3.3 Specimen shipment

See the Manual of Procedures for instructions regarding transport or shipment of specimens to the genome sequencing centers and to the blood specimen repository.

Protocol Template

7 UNANTICIPATED PROBLEMS AND SERIOUS ADVERSE EVENTS

The methods of specimen collection in this microbiome sampling study pose only minimal risk to the study subjects. As defined in 45 US Code of Federal Regulations (CFR) 46.102 (i), “Minimal risk means that the probability and magnitude of harm or discomfort anticipated in the research are not greater in and of themselves than those ordinarily encountered in daily life or during the performance of routine physical or psychological examinations or tests.” The minimal physical risks associated with the sampling procedures are described in Section 2.3.1 and in the informed consent document.

The nature of the information collected from subjects may involve risk to their privacy. These risks are described in Section 2.3.1 and in the informed consent document. Appendices A and B contain tables and a flowchart that address the disposition and access issues for original specimens as well as the isolated DNA, possible cell lines, and sequence data that may be derived from the original specimens.

The results of research cannot be foreseen, so it is possible that unanticipated problems may arise in the study. In addition to unexpected adverse events, there are other types of incidents, experiences, and outcomes that occur during the conduct of human subjects research that represent unanticipated problems but are not considered adverse events. For example, some unanticipated problems involve social or economic harm instead of the physical or psychological harm associated with adverse events. The investigator or designee is responsible for the detection and documentation of unanticipated problems and Serious Adverse Events (SAE) in subjects participating in the study. Unanticipated problems and SAEs should be reported to the Clinical Data Coordinating Center (CDCC) and to the IRB as outlined in the following sections and in the Manual of Procedures.

7.1 Definition of an Unanticipated Problem

The Office for Human Research Protections (OHRP), Department of Health and Human Services (DHHS) considers unanticipated problems, in general, to include any incident, experience, or outcome that meets **all** of the following criteria:

- unexpected (in terms of nature, severity, or frequency) given (a) the research procedures that are described in the protocol-related documents, such as the IRB-

approved research protocol and informed consent document; and (b) the characteristics of the subject population being studied;

- related or possibly related to participation in the research (*possibly related* means there is a reasonable possibility that the incident, experience, or outcome may have been caused by the procedures involved in the research); and
- suggests that the research places subjects or others at a greater risk of harm (including physical, psychological, economic, or social harm) than was previously known or recognized.

An incident, experience, or outcome that meets the three criteria above generally will warrant consideration of substantive changes in the research protocol or informed consent process/document or other corrective actions in order to protect the safety, welfare, or rights of subjects or others. Examples of corrective actions or substantive changes that might need to be considered in response to an unanticipated problem include:

- changes to the research protocol initiated by the investigator prior to obtaining IRB approval to eliminate apparent immediate hazards to subjects;
- modification of inclusion or exclusion criteria to mitigate the newly identified risks;
- implementation of additional procedures for monitoring subjects;
- suspension of enrollment of new subjects;
- suspension of research procedures in currently enrolled subjects;
- modification of informed consent documents to include a description of newly recognized risks; and
- provision of additional information about newly recognized risks to previously enrolled subjects.

7.2 Reporting of Unanticipated Problems

Institutions engaged in human subjects research conducted or supported by DHHS must have written procedures for ensuring prompt reporting to the IRB, appropriate institutional officials, and any supporting department or agency head of any unanticipated problem involving risks to subjects or others (45 CFR 46.103(b)(5)). Furthermore, for research covered by an assurance approved for federalwide use by OHRP, DHHS regulations at 45 CFR 46.103(a) require that institutions promptly report any unanticipated problems to OHRP.

Incidents or events that meet the OHRP criteria for unanticipated problems require the completion of an unanticipated problem report form. OHRP recommends that investigators include the following information when reporting an adverse event, or any other incident, experience, or outcome as an unanticipated problem to the IRB:

- appropriate identifying information for the research protocol, such as the title, investigator's name, and the IRB project number;
- a detailed description of the adverse event, incident, experience, or outcome;
- an explanation of the basis for determining that the adverse event, incident, experience, or outcome represents an unanticipated problem;
- a description of any changes to the protocol or other corrective actions that have been taken or are proposed in response to the unanticipated problem.

For multicenter research protocols, if a local investigator at one institution engaged in the research independently proposes changes to the protocol or informed consent document in response to an unanticipated problem, the investigator should consult with the study sponsor or coordinating center regarding the proposed changes because changes at one site could have significant implications for the entire research study.

Forms describing unanticipated problems will be submitted to the CDCC and the IRB. The CDCC will notify the NIH study representative of the unanticipated problem. Unanticipated problems will be reported immediately to the NIH Clinical Studies Oversight Committee (CSOC). The CSOC may convene an *ad hoc* meeting for review of the unanticipated problem and consideration of corrective actions. Other supporting documentation of the problem may be requested by the CSOC and should be provided as soon as possible. A summary of the CSOC meeting and proposed actions will be provided to the study Steering Committee. The study PIs will then submit the CSOC review and any protocol changes to the IRBs.

Investigators will be responsible for reporting unanticipated problems from the time that the first subject is enrolled until one year after the final subject is enrolled.

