4 STUDY DESIGN OVERVIEW

This study is designed to collect specimens from healthy adults from five body sites: the oral cavity, skin, nasal cavity, gastrointestinal tract, and vagina (female subjects only). Originally, the total enrollment target for the study was 250 subjects. Preliminary data analyses have yielded information regarding inter-individual and intra-individual variation in the composition of the microbiome. The extent of intra-individual variation between visits 1 and 2 is body site-dependent, and has generated interest in additional sampling efforts. As the study approaches the successful recruitment of 250 healthy, adult subjects in St. Louis and Houston, the study Steering Committee has decided to expand the study in two basic ways. First, additional individuals (25 per site) will be enrolled, so that a total of 300 subjects will be sampled. This enhancement represents an increase of 20 percent in total subjects sampled, so that compositional data from multiple body sites are even more robust. Secondly, the study will add a third sampling of 100 subjects (50 per site). A third sampling will enable investigators to study intra-individual variation during an extended time period, and intra-individual variation among different body sites can be analyzed more comprehensively.

More than 300 interested individuals will need to be screened in order to derive approximately 300 eligible subjects. The study will be phased, with 50 eligible subjects participating in an initial pilot phase and having four or five body sites sampled as well as having a blood specimen collected. Following evaluation of the operational aspects of the pilot phase, approximately 250 additional eligible subjects will be enrolled and these subjects will have up to five of the same body sites sampled and will have a blood specimen drawn.

Individuals involved in the study will be between the ages of 18 and 40 and sampling will include an approximately equal number of males and females, with a goal of at least 20% representation from minority populations. Subjects will be contacted to have the same body sites sampled a second time within approximately 1 year of the first sampling. Approximately 100 subjects (50 subjects from each of the two sites) will be contacted to have the same body sites sampled a third time within approximately 6 months of the second sampling.

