6 STUDY PROCEDURES/EVALUATIONS

6.1 Outline of Study Procedures

Visit Timing Sampling Timepoint	Screening Days -30 to -2 Pre-Enrollment	Visit 1 Day 0 Baseline Sampling Visit	Visit 2, Day 30 – 365 Visit 3, Day 60 - 548 Re-Sampling Visits (for subjects who are available for re- sampling)
Pre-screening contact : Review study information sheet with interested individual	X		
Obtain informed consent	X		
Reaffirm consent		X	X
Assign screening number	X		
Perform/review history and physical exam	X	X	X
Vital signs or oral temperature (See Section 6.2)	X	X	X
Record concomitant medications	X	X	X
Vaginal pH	X	X	X
Collect blood for HIV, HBV, HCV	X		
Urine pregnancy test for females	X	X	X
Counsel subjects on refraining from using products and preparation for sampling visit	X		X
Instruct subjects on stool collection and provide stool collection kit	X		X
Inform subjects of a third sampling possibility and obtain contact information if subject agrees to be contacted			X
Specimen Collection	Body Site Specimen Collection		X
	Blood Specimen Collection		X
	Obtain Stool specimen		X
Subsequent Research Laboratory Processes	Microbial Nucleic Acid Isolation, Quantitation, and Evaluation		X
	Microbial Nucleic Acid Sequence Generation and Data Deposition in Repositories		X
Other Procedures	Blood to Coriell Institute for human DNA isolation/storage, later lymphoblastoid cell line transformation; serum stored in clinical lab		X

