8.3 Subject Enrollment and Follow-Up

This study will consent and enroll approximately 300 subjects. Subjects who are sampled at two visits could be enrolled in the study for up to 1 year. Approximately 100 subjects (50 at each site) who are sampled a third time could be enrolled in the study for up to 18 months. It is anticipated that subject retention will rely on the interest of the subjects in the study as well as on reimbursement for their time and effort.

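### The Section 7.2 period for reporting unanticipated problems covers every permitted Visit 2 but not every permitted Visit 3

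*Protocol*

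**What the plan says.** Section 7.2 of the Protocol closes with the period of responsibility: investigators answer for "reporting unanticipated problems from the time that the first subject is enrolled until one year after the final subject is enrolled". Earlier in the same section, report forms go to the Clinical Data Coordinating Center (CDCC) and the IRB, the CDCC informs the NIH representative, and the problem goes to the NIH Clinical Studies Oversight Committee (CSOC).

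The visit schedule in Section 6.1 gives "Visit 2, Day 30 – 365" and "Visit 3, Day 60 - 548", both counted from Visit 1 at Day 0. Section 6.2 repeats the two windows. Section 4 describes the intervals in words. For the second sampling: "Subjects will be contacted to have the same body sites sampled a second time within approximately 1 year of the first sampling". About 100 subjects "will be contacted to have the same body sites sampled a third time within approximately 6 months of the second sampling". Section 8.3 gives the resulting length of participation: "Approximately 100 subjects (50 at each site) who are sampled a third time could be enrolled in the study for up to 18 months". For subjects with two visits it gives up to one year.

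Serious adverse events have a separate rule in Section 7.4, tied to sampling or to the 48 hours around a study visit and not to a date after the last enrolment.

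**The concern.** The one-year limit equals the longest participation of a subject with two visits. It is six months shorter than the longest participation of a subject with three. A subject enrolled near the end of accrual can therefore attend a permitted Visit 3 after the protocol's stated reporting duty has ended.

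Unanticipated problems are wider than serious adverse events. Sections 7 and 7.1 include social, economic and psychological harm and incidents that are not adverse events at all. Section 2.3.1 gives much of its space to privacy risk. A privacy breach would usually not be a serious adverse event and need not occur within 48 hours of a visit, so the rule in Section 7.4 does not stand in for the one in Section 7.2.

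**Working it through.** **Inputs**
- End of the reporting duty: one year, taken as 365 days, after the last enrolment (Section 7.2).
- Visit 2: Day 30 to Day 365. Visit 3: Day 60 to Day 548 (Sections 6.1 and 6.2).
- Visit 3 within about 6 months of Visit 2, taken as 183 days (Sections 3, 4 and 6.2).
- Enrolment is taken as Day 0, because the schedule in Section 6.1 labels screening as pre-enrolment.

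**1. The plan's own figure.** The last permitted Visit 2 plus six months is 365 + 183 = 548, and 18 × 365.25/12 = 547.9. Day 548 is therefore consistent with the 18 months of Section 8.3.

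**2. Visit 2.** For the last enrollee, 365 − 365 = 0 days fall outside. Every permitted Visit 2 is covered.

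**3. Visit 3, last enrollee.** 548 − 365 = 183 days fall outside. The Visit 3 window has 548 − 60 + 1 = 489 days, so 183/489 = 37% of it lies after the duty ends.

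**4. Visit 3, earlier enrollees.** For a subject enrolled L days before the last one, the duty ends on that subject's Day 365 + L. The largest gap is max(0, 548 − 365 − L).

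| L (days before last enrolment) | Largest gap (days) |
|---|---|
| 0 | 183 |
| 30 | 153 |
| 91 | 92 |
| 183 or more | 0 |

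**5. Dependence on Visit 2.** Visit 3 can be no later than 183 days after Visit 2. With Visit 2 on Day v, the gap is at most max(0, v + 183 − 365 − L) = max(0, v − 182 − L). For the last enrollee (L = 0):
- v = 182 gives 0 days.
- v = 270 gives 88 days.
- v = 365 gives 183 days.

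The gap opens only if Visit 2 falls after about Day 182, and it reaches its full size only if Visit 2 falls on Day 365.

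**6. Calendar limit.** The Protocol Summary and Section 4 put enrolment and collection together at about 18 months. Suppose this were a hard limit and the last enrolment came at month m. Both are assumptions, since the documents give no date of last enrolment. The duty then ends at month m + 12, and the gap is max(0, 18 − (m + 12)) = max(0, 6 − m) months. That is 3 months at m = 3 and none from m = 6. Under the same limit, however, a subject enrolled at month m has only 18 − m months for all visits, so no subject enrolled after the start could use the full window to Day 548.

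**7. Start of the clock.** If enrolment were counted from screening (Day −2 to Day −30), the largest gap would be 548 − (−2 + 365) = 185 to 548 − (−30 + 365) = 213 days.

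**The case against.** The strongest answer is that other duties remain in force. Section 7 makes the investigator responsible for detecting and documenting unanticipated problems in participating subjects, and a subject at Visit 3 is participating. Section 7.2 requires a report form for every event that meets the federal criteria and cites an institutional duty of prompt reporting. Section 10.2 requires that the IRB be told of new information bearing on subject safety. None of these carries an end date. Section 7.4 covers serious adverse events at Visit 3 whenever that visit falls. Sampling is described as minimal risk, and the Visit 3 procedures in Section 6.2 list no blood draw.

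Most of this stands, and it limits the point. A reader might infer that a non-serious harm at a late Visit 3 need reach nobody. The documents do not support that, because the general duties to the IRB continue. What they do not settle is the study-level route. The steps to the CDCC and the CSOC are laid out in Section 7.2, and the only sentence there that fixes the period of the investigators' duty ends it at one year. Section 7.2 is thus open-ended in one place and closed in another.

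A reader might also infer that about 100 subjects are exposed. That is the planned number of third samplings, not the number with a late Visit 3 among the last enrollees. Nor are the 50 added subjects the third-sampling group: Section 4 draws that group from subjects who gave a second set of specimens.

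The calendar argument could shrink the gap or remove it, but only by setting the approximate study duration against the Day 548 window. It moves the conflict without resolving it.

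**Conclusion.** The inconsistency is real and modest. The stated reporting period covers every permitted Visit 2 but not every permitted Visit 3, and no other section extends it. The shortfall is at most 183 days, with enrolment counted from Day 0. It applies only to third-sampling subjects enrolled within 183 days of the last subject whose Visit 2 was late enough to put Visit 3 beyond the limit. A late Visit 2 is foreseeable, since Section 6.2 lets it be postponed after use of an excluded drug as long as it stays within one year. How many subjects meet these conditions cannot be worked out, because the documents give no enrolment dates.

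What lapses is the explicit investigator duty for non-serious, privacy, social or economic problems, including its route to the CDCC and the CSOC. No outcome, sample size or analysis is affected. It would go too far to call this a design flaw that must be fixed before the study can proceed, given the continuing IRB duties, the separate rule for serious events and the minimal-risk procedures.

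**What to change.** Reword the last sentence of Section 7.2 so that the reporting period runs at least until the last study visit, including Visit 3, of the last subject. Reconcile it with the visit windows in Sections 6.1 and 6.2 and with the length of participation in Section 8.3. If a fixed interval after the last enrolment is preferred, it must be at least 548 days to cover the window as written, which is 183 days longer than now.

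The cost is one sentence in an amendment and up to about six more months of reporting duty.

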7.3 Definition of a Serious Adverse Event

The OHRP, DHHS defines an Adverse Event (AE) as any untoward or unfavorable medical occurrence in a human subject, including any abnormal sign (for example, abnormal physical exam or laboratory finding), symptom, or disease, temporally associated with the subject's participation in the research, whether or not considered related to the subject's participation in the research (modified from the definition of adverse events in the 1996 International Conference on Harmonisation E6 Guidelines

for Good Clinical Practice). A Serious Adverse Event/Experience (SAE) is any adverse event/experience that meets any of the following criteria:

- Results in death
- Is life-threatening (places the subject at immediate risk of death from the event as it occurred)
- Requires inpatient hospitalization or prolongation of existing hospitalization
- Results in a persistent or significant disability or incapacity
- Results in congenital anomaly/birth defect
- Any other adverse event that, based upon appropriate medical judgment, may jeopardize the subject and may require medical or surgical intervention to prevent one of the other outcomes listed in this definition.

For those events meeting the definition of Serious Adverse Events, the completion of an SAE form is required.

7.4 Reporting of Serious Adverse Events

OHRP considers adverse events that are unexpected, related or possibly related to participation in research, and *serious* to be the most important subset of adverse events representing unanticipated problems, because such events always suggest that the research places subjects or others at a greater risk of physical or psychological harm than was previously known or recognized, and routinely warrant consideration of substantive changes in the research protocol or informed consent process/document or other corrective actions in order to protect the safety, welfare, or rights of subjects. Furthermore, OHRP notes that IRBs have authority to suspend or terminate approval of research that, among other things, has been associated with unexpected serious harm to subjects (45 CFR 46.113). In order for IRBs to exercise this important authority in a timely manner, they must be informed promptly of those adverse events that are unexpected, related or possibly related to participation in the research, and serious (45 CFR 46.103(b)(5)).

All serious adverse events will be:

- recorded on the appropriate serious adverse event case report form;
- followed until satisfactory resolution or until the Principal Investigator or Subinvestigator deems the event to be chronic or the patient to be stable;

- reported to the IRB and to the CDCC;
- entered in the CDCC data management system.

Any adverse event considered serious by the Principal Investigator or Sub-investigator or which meets the aforementioned criteria must be submitted on an SAE form to the CDCC. Investigators will be responsible for reporting SAEs that occur during sampling or within 48 hours of a study visit.

The study clinician will complete a Serious Adverse Event Form within the following timelines:

- All deaths and immediately life-threatening events, whether related or unrelated, will be recorded on the Serious Adverse Event Form and sent by fax within 24 hours of site awareness.
- Serious adverse events other than death and immediately life-threatening events, regardless of relationship, will be reported via fax within 72 hours of site awareness.

The CDCC will notify the NIH study representative of the serious adverse event within one business day. SAEs that are related to study participation will be reported immediately to the NIH CSOC. The CSOC may convene an *ad hoc* meeting for review of the SAE and consideration of corrective actions. Other supporting documentation of the event may be requested by the CSOC and should be provided as soon as possible. A summary of the CSOC meeting and proposed actions will be provided to the study Steering Committee. The study PIs will then submit the CSOC review and any protocol changes to the IRBs.

Serious adverse events that are considered unrelated to study participation will be provided to the CSOC in a line listing to be reviewed at regularly scheduled meetings.

